6.4. Cell manipulation and gene transfer with the lentiviral vector

6.4.1. BM CD34+ cell purification

Patients' HSC manipulation will be performed by MolMed S.p.A. in GMP conditions. The collected marrow will be diluted, stratified with lymphoprep and centrifuged in order to separate blood fractions. Final cell suspension primarily made of MNC will be collected. Positive selection on BM will be performed using immunomagnetic beads (CliniMACS, Miltenyi) and an immunomagnetic enrichment device. WBC counts will be performed in basal BM samples from each marrow bag, after buffy coat collection and both in the positive and negative cell fraction. Phenotypic expression of surface molecules (CD34) will be determined by direct labeling using standard methodology. After centrifugation to reduce volume, the negative fraction will be collected in divided bags with DMSO, frozen and stored in liquid nitrogen for possible infusion if engraftment failure will occur. Samples from each bag will be sent for detecting bacterial contamination.

6.4.2. Lentiviral vectors

Autologous bone marrow CD34⁺ cells will be transduced with a clinical grade LV containing WAS gene. In this construct (w1.6W), the WAS gene is designed under the control of WAS autologous promoter. The w1.6W vector is further modified by introducing a mutation in the WPRE element. Viral supernatants will be produced in a GMP facility of the biotech company, MolMed S.p.A. (Milan, Italy).

6.4.3. Gene transfer of BM CD34+ cells

Purified CD34+ cells will be seeded in retronectin coated bags and further incubated for 24 hours at 37°C in CO₂ in serum free medium (Cell Grow) supplemented with the cytokines SCF, TPO, FLT3-L and IL-3. At the end of the incubation period, the cells will be transduced in the presence of cytokines with the LV-WASP vector. Two rounds of transduction are foreseen, each

lasting about 16 hours in the presence of 1×10^8 TU/ml of LV (corresponding to a Multiplicity of Infection – MOI - of 100), with a washout time of 12 hours, for a total of about 68 hours of *in vitro* culture. Since the cells will be freshly infused, only tests for endotoxin, mycoplasma, large T antigen DNA, and immunophenotype characterization will be completed and results will be available at the infusion time. The validated Hospital Sterility test (BacT/ALERT) is performed to allow a shorter response time and intermediate results will be available at the time of infusion. The detailed tests and specifications of the drug substance and drug product are reported in the investigator's brochure. At the end of the transduction procedure, the transduced CD34⁺ cells will be harvested, washed with saline and resuspended in a minimum of 20 ml saline solution at the concentration of 10×10^6 /ml. The final drug product will consist of a cell suspension containing the transduced CD34⁺ cells in a sterile syringe(s) or bag(s) of the suitable volume.

If the cells are detected to be contaminated, the medicinal product will not be returned to the patient and the patient will receive the unmanipulated back-up. If a positive result is obtained for the sterility test after the infusion, the patient will receive a specific antibiotic treatment and will be strictly monitored.

6.4.4. Gene transfer of MPB CD34+ cells

Mobilized peripheral blood (MPB) CD34⁺ cells may be used as cell source of genetically modified cells. Transduction will be performed as described above for BM CD34⁺ cells, starting from the previously stored CD34⁺ cells obtained from leukapheresis.

MPB may be used as single cell source:

- 1) in case of older patients (> 5 years old) to increase the dose of infused cells, if the expected collection from bone marrow is predicted not be sufficient to achieve the optimal target dose or for clinical reasons.
or
- 2) in case the patient has initiated conditioning and the transduced bone marrow CD34⁺ cells cannot be released for infusion. In this case the day of infusion will be postponed accordingly.

A mixture of MPB and BM CD34⁺ cells can be administered if required to obtain a sufficient cells dose.

6.5. Conditioning regimen

A reduced intensity-conditioning regimen will be administered before the autologous-engineered cells infusion based on the rationale described in chapter 5.

We will combine iv Busulfan (bodyweight-based and AUC targeted dose, see below, 8 +/- 1 doses administered consecutively from days -3 to -1), Fludarabine (total dose 60 mg/sqm, on days -3 and -2) and Rituximab (375 mg/sqm in single dose, on day -22).

Iv ATG Thymoglobulin may be used at PI discretion in patients with clinical autoimmunity before day-18 as an additional lympho-depleting agent to eliminate auto-reactive memory T cells.

Clinical data from the ADA-SCID trial indicate that the dose of administered CD34+ cell is one of the important factors in determining the engraftment of transduced progenitors, and thus the outcome of gene therapy. HSC freezing is associated to a significant reduction of the overall cell number, further increased by the mortality consequent to transduction. Thus, with the aim of preserving the maximum absolute number of CD34⁺ cells, we will avoid freezing the transduced cells.

Since our protocol is based on the transduction and re-infusion of freshly isolated CD34⁺ cells, the window of time between harvesting and transplantation will be limited to the minimum. The interval between the last infusion of drug and cell infusion will be sufficient to reduce drug concentration to safe levels for Busulfan (24-26 hours wash out) and Fludarabine (50-54 hours wash out).

6.5.1. Busulfan

Based on our experience in combining *ex vivo* gene therapy with reduced intensity in the 15 patients enrolled in the ADA-SCID gene therapy trial and previous pilot studies, we will adopt intravenous Busulfan (Busilvex) as myelotoxic drug. The alkylant will be administered at a higher dose than in ADA-SCID trial, because a significant level of myeloid engraftment can be a requirement for platelet correction in WAS patients.

Patients will receive one of five bodyweight-based doses of intravenous busulfan, according to the following scheme:

Table 6 Busulfan dosage according to patient's weight

< 9 kg	9 to < 16 kg	16-23 kg	> 23 – 34 kg	> 34 kg
1 mg/kg/dose	1.2 mg/kg/dose	1.1 mg/kg/dose	0.95 mg/kg/dose	0.8 mg/kg/dose

Patients will receive a total of 8 (+1) doses, given every 6 hours from day -3 to day -1. The dose of Busulfan and the number of doses may be adjusted to reach the target AUC (see below).

The mean half-life of i.v. Busulfan ranges between 2.83 to 3.90 hours.

We will monitor Busulfan plasmatic levels by temporized sampling following infusion after the first and the sixth dose.

The exposure to Busulfan, based on pharmacokinetic profiling, will be defined by the Pharmacological Institute of the University of Pavia. The dose of Busulfan will be adjusted to avoid excessive toxicity or insufficient exposure, aiming at a target AUC of 6000 ng/ml*h, equivalent to a cumulative target AUC of 48000 ng/ml*h ([Malar R, et al. 2011](#)). This value is equivalent to 53% of the myeloablative dose exposure (90000 ng/ml*h). Thus, in order to achieve this target cumulative dose of Busulfan, the fifth and the following doses will be adjusted according to the AUC obtained after the first dose. In particular, in case the estimated total target AUC \pm 4000 ng/ml*h is achieved already after the 4th dose, the administration of the following doses will be stopped. In case a lower AUC is detected at the first dose, the fifth and next doses should be increased both to reach the target AUC as well to replenish the reduced Busulfan exposure in the first four doses.

A dose adjustment will be performed if total predicted AUC shows more than 10% deviation from the target (total predicted AUC is < 43200 ng/ml*h or > 52800 ng/ml*h).

Dose adjustment calculation: $D5 = D1 * (\text{target AUC} - \text{AUC1} * 4) / (\text{AUC1} * 4)$

$D5 = 5^{\text{th}}$ dose (mg)

$D1 = 1^{\text{st}}$ dose (mg)

$\text{AUC1} = \text{AUC}_{0-\infty}$ after first dose

In case the total cumulative target is not reached after 8 doses, an additional dose may be administered according to the following calculation:

$D9 = D5 * [\text{target AUC} - (\text{AUC1} * 4 + \text{AUC6} * 4) / \text{AUC6}]$

$D9 = 9^{\text{th}}$ dose (mg)

$\text{AUC6} = \text{AUC}_{0-6\text{h}}$ after sixth dose

In case of administration of a ninth dose of Busulfan, the cell infusion will be scheduled to allow a wash-out time of 24 hours from the last dose.

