8.2 Demographic and Baseline Variables

Demographic data and other baseline characteristics will be presented for the ITT set.

The following demographic and other baseline characteristics will be summarised and listed for this study:

- Age (years) - calculated relative to date of gene therapy
- Age group
 - 0 to <28 days
 - 28 days to <24 months
 - ≥24 months to 11 years
 - <11 years
- Age group 2
 - < 5 years
 - ≥ 5 years
- Sex
- Race
- Ethnicity
- Height (cm)
- Weight (kg)

- BMI (kg/m²)
- Body Surface Area (m²)
- Country of residence
- Time since diagnosis (years) - calculated relative to date of consent
- Derivations for demographic data are included below:
 - BMI (kg/m²) = weight (kg) / height (m)²
 - Body Surface Area (m²) = $\sqrt{\frac{\text{weight}(\text{kg}) \times \text{height}(\text{cm})}{3600}}$
- Busulfan cumulative AUC (note that busulfan will only be summarised in the conditioning regimen output [see Section 12] and will not be summarised with demographics):
If subject receives 8 doses of busulfan ($AUC1 + AUC6) \times 4$
If subject receives 9 doses of busulfan ($AUC1 + AUC6) \times 4 + \frac{AUC6 \times D9}{D5}$
Where $AUC1 = AUC(0-\infty)$ from first dose, $AUC6 = AUC(0-6 \text{ h})$ from 5th or 6th dose, D5 is the 5th dose and D9 is the 9th dose

A listing will also be created for the length of hospitalisation for gene therapy.

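### The ninth busulfan dose formula in Protocol 6.5.1 has a misplaced bracket: as printed it gives D9/D5 of about 48,000 whatever the exposure shortfall

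*Protocol*

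**What the plan says.** Protocol section 6.5.1 doses busulfan to exposure, "aiming at a target AUC of 6000 ng/ml*h" per dose, "equivalent to a cumulative target AUC of 48000 ng/ml*h" over eight doses. It has two steps for correcting the dose.

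- **Fifth dose.** "A dose adjustment will be performed if total predicted AUC shows more than 10% deviation from the target", that is, outside 43,200 to 52,800 ng/ml*h. The new dose is D1 times the bracketed quantity (target AUC − 4 × AUC1), divided by (4 × AUC1).
- **Ninth dose.** "In case the total cumulative target is not reached after 8 doses, an additional dose may be administered according to the following calculation". The printed line is `D9 = D5 × [target AUC − (AUC1×4 + AUC6×4) / AUC6]`, with the square bracket closing after AUC6.

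SAP section 8.2 defines the cumulative AUC to be reported. For the case headed "If subject receives 9 doses of busulfan" it uses `(AUC1 + AUC6) × 4 + AUC6 × D9 / D5`.

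**The concern.** A make-up dose should be proportional to the exposure still missing. In the printed line, division binds before subtraction, so AUC6 divides only the eight-dose sum. The result is an AUC in ng/ml*h minus a pure number, which is dimensionally invalid and hardly moves with the shortfall.

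This is the protocol's only rule for sizing an extra dose of the myelotoxic drug in the conditioning regimen. Anyone applying it has to replace it with a formula that the protocol does not contain, and an auditor cannot reproduce an administered ninth dose from the text.

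**Working it through.** **Inputs from the documents.** Target T = 48,000 ng/ml*h, the fifth-dose and ninth-dose formulas and the adjustment limits (Protocol 6.5.1); nine-dose exposure (SAP 8.2); starting dose of 1.2 mg/kg for 9 to <16 kg (Protocol Table 6). The documents give no patient AUC values, so AUC1 and AUC6 below are assumed.

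**The section's other figures reproduce.**
- 8 × 6,000 = 48,000.
- 48,000 / 90,000 = 53%.
- 0.9 × 48,000 = 43,200 and 1.1 × 48,000 = 52,800.
- The fifth-dose formula at AUC1 = 6,000 gives (48,000 − 24,000) / 24,000 = 1, so no change, as it should.

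**Ninth dose as printed.** D9/D5 = T − (4×AUC1 + 4×AUC6)/AUC6 = 48,000 − 4 × (AUC1/AUC6 + 1).

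Only the ratio AUC1/AUC6 enters. At AUC1 = AUC6 the result is 48,000 − 8 = 47,992. It is 47,988 when AUC1/AUC6 = 2 and 47,994 when it is 0.5.

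**Intended form.** Under dose proportionality, which the fifth-dose rule also assumes, a dose D9 adds AUC6 × D9/D5. Setting the SAP nine-dose total equal to T:

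4×(AUC1 + AUC6) + AUC6 × D9/D5 = T, so D9/D5 = [T − 4×(AUC1 + AUC6)] / AUC6.

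This has the same structure as the fifth-dose formula: the whole shortfall is bracketed and then divided.

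| AUC1 | AUC6 | Eight-dose sum | Shortfall | Printed D9/D5 | Corrected D9/D5 |
|---|---|---|---|---|---|
| 6,000 | 6,000 | 48,000 | 0 | 47,992 | 0 |
| 5,900 | 5,900 | 47,200 | 800 | 47,992 | 0.14 |
| 5,700 | 5,700 | 45,600 | 2,400 | 47,992 | 0.42 |
| 5,500 | 5,500 | 44,000 | 4,000 | 47,992 | 0.73 |
| 5,400 | 5,400 | 43,200 | 4,800 | 47,992 | 0.89 |
| 5,000 | 6,500 | 46,000 | 2,000 | 47,993 | 0.31 |

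In the first five rows the predicted total is at or above 43,200, so no fifth-dose change is triggered and D5 = D1. In the last row AUC1 = 5,000 predicts 40,000, so D5/D1 = (48,000 − 20,000)/20,000 = 1.4 and the expected AUC6 is 7,000; the row supposes that 6,500 is observed.

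**Put back into the SAP formula.** The corrected ratio returns 48,000 in every row, for example 44,000 + 5,500 × (4,000/5,500) = 48,000. The printed ratio at 5,400/5,400 returns 43,200 + 5,400 × 47,992 = 259,200,000.

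**In milligrams.** For an assumed 10 kg child with D5 = 12 mg and AUC1 = AUC6 = 5,400, the printed line gives 12 × 47,992 = 575,904 mg. The corrected line gives 12 × 4,800/5,400 = 10.7 mg.

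**Alternative reading.** Taking the target as the per-dose 6,000 does not rescue the line: at AUC1 = AUC6 the ratio is 6,000 − 8 = 5,992.

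**The case against.** Several points can be made against giving this weight.

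- **It may be an artefact of text extraction.** The formula was read from a PDF, and a fraction bar may have been lost. This cannot be excluded. However, the line is complete, its brackets balance, the fifth-dose formula beside it was read correctly, and a stacked fraction in SAP 8.2 survived as a fraction.
- **The figure of 48,000 measures no real dosing error.** It depends on the unit: with the target written as 48 mcg/ml*h, the same line gives about 40 at AUC1 = AUC6. That is true, but such dependence on units is itself a sign that the formula is invalid.
- **The SAP check is circular**, because the correction was solved from the SAP formula. As a numerical check it is. The fifth-dose rule and the stated purpose of the dose support the same form independently.
- **Specialists would see the intent.** The section assigns exposure profiling to an external pharmacology institute, and the ninth dose is optional. The documents do not say who computes D9, so it may well have been calculated correctly in practice.
- **Dosing is probably over.** The study started in April 2010 with five years of enrolment, and protocol version 12 dates from September 2023. If all patients have been treated, what remains is the record, the audit of any ninth dose, and the risk of the line being copied into a later protocol.

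These points limit the consequences. None makes the printed line correct.

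**Conclusion.** The concern holds. As printed, the ninth-dose rule gives a ratio of about 48,000 at any shortfall, including zero, and cannot be followed. The intended ratio over the assumed AUC values runs from 0 to 0.89. The AUC values are illustrative, but the conclusion hardly depends on them, since the printed ratio changes by only a few units in 48,000. It does rest on the bracket standing in the source document as it does in the extracted text.

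This is an error in one operative dosing line, not a conflict of method between the protocol and the SAP. The SAP cumulative-AUC formula and the busulfan exposure plots use the dose actually given, so no endpoint, estimate or interval changes. Nothing in the documents shows that a ninth dose was given, or that one was miscalculated.

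**What to change.** 1. Check the line against the source PDF.
2. If the bracket stands there as extracted, replace the line with `D9 = D5 × [target AUC − (AUC1×4 + AUC6×4)] / AUC6`, and state that target AUC here means the cumulative 48,000 ng/ml*h.
3. Have the pharmacology group confirm the corrected line and the formula actually used.
4. Review the calculation for any patient who received a ninth dose; with eight planned patients, this is at most eight records.

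The cost is one bracket, one confirmation and a short record check. The SAP needs no change.

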6.5.2. Fludarabine

Fludarabine is a nucleoside analogue, currently included in non-myeloablative preparative regimens for HSCT as a drug inducing abrogation of lymphoid precursors in the bone marrow. Fludarabine is commonly used in conditioning regimen with a dose scheme ending at day -3 or -2 before reinfusion of donor HSC at a total dose of 60 mg/sqm. In the peripheral compartment, Fludarabine targets both resting and proliferating lymphocytes, producing a significant lymphopenia of B and T cells. It has been described that CD20^+ B cells, CD4^+ T cells (mainly naive ($\text{CD4}^+ \text{CD45RA}^+$) T cells) and CD8^+ T cells decrease profoundly upon Fludarabine treatment. Its half-life is 9.6 hours (3.1-26) measured in adult patients undergoing transplant ([Jacobson 2005](#)).

Table 7 Gene therapy schedule for WAS patients

DAY	*	-22	-20	-19	-18	-03	-02	-01	0
PBSC back-up \pm CD34+ cell collection		■							
BM harvest ***						■			
iv RITUXIMAB 375 mg/sqm/day			■						
iv BUSULFAN Dose: see below							■	■	
iv FLUDARABINE 30 mg/sqm/day						■	■		
ATG THYMOGLOBULINE ** 2,5 mg/kg/day			■	■	■				
Infusion of transduced CD34+ cells								■	

Busulfan bodyweight-based and AUC targeted dose, to be given every 6 hours for 8 doses (+/- 1) as described above (see [Table 6](#)).

*Usually performed about 5-10 weeks before treatment. BM collection is performed, if PBSC mobilization is not suitable.

**Iv ATG Thymoglobulin may be used at PI discretion in patients with clinical autoimmunity.

*** BM harvest is not performed if MPB is used as the only cell source for transduction

6.5.3. Rituximab

Rituximab, a monoclonal antibody directed against the CD20 molecule found on pre-B cells and mature B cells, was introduced in the late 1990s for the treatment of non-Hodgkin's lymphoma. Recently, this antibody has been used to treat autoimmune diseases, especially those associated with a prominent humoral component and with potentially pathogenic autoantibodies. Small cohort studies have indicated that rituximab could have an important role in the management of these disorders. Rituximab has also been utilized in the transplant setting, to diminish levels of alloreactive antibodies in highly sensitized patients, to manage ABO-incompatible transplants, and to treat rejection associated with B cells and antibodies. The exact mechanism by which rituximab exerts its effects in autoimmunity and transplantation remains unclear, as specific autoantibody or alloantibody levels often seem not to diminish in parallel with clinical improvement. A role for rituximab in depleting B cells and compromising their antigen-presenting function seems likely; rituximab might also inhibit T-cell activation. Rituximab has been successfully used to treat lymphoproliferative disorder following solid organ transplantation and is commonly employed as pre-emptive therapy for EBV-induced lymphoproliferation in the context of allogeneic HSCT. Rituximab will be used at 375 mg/sqm in a single dose on day -22.

6.6. Safety considerations on the procedure and conditioning regimen

Patients will undergo blood tests before and during treatment and in the follow up phase. In case blood removal will occur through venipuncture, the risks of these procedures are pain, formation of hematoma and minimal risk of infection at the puncture site. Blood tests will be planned on different days to minimize the risks of anemia due to blood loss.

Standard risks associated with implantation of a central venous catheter, collection of stem/progenitor cells by means of apheresis, and BM harvest under general anesthesia are to be taken into consideration ([Moog et al. 2001](#); [Nishimori et al. 2001](#); [Mattioli et al. 2007](#)). In particular, the risks of central catheter implantation include bleeding, formation of hematoma, pain, infections and rarely pneumothorax. The possible side effects of G-CSF administration for mobilization of CD34+ cells in the peripheral blood include fever, pain, and rarely allergic type reactions. Overall the safety record of G-CSF is very good, apart from extremely rare reports of spontaneous splenic ruptures. Plerixafor is registered for use in adults. The most common adverse reactions reported in patients in conjunction with G-CSF were diarrhea, nausea, fatigue, injection site reactions, headache, arthralgia, dizziness and vomiting. The safety and efficacy of its use in children has not been studied in controlled clinical trials; several single centers studies reported no major adverse events with plerixafor administration in children ([Pham HP et al. 2012](#); [Son MH et al. 2013](#); [Hong KT et al. 2012](#); [Sevilla J et al. 2012](#)).

Adverse reactions to leukapheresis can derive from transient volume loss, and lowering of calcium levels by the citrate anticoagulant. BM harvest can be associated with bleeding, formation of haematoma, pain, infections and those correlated with general anesthesia.

The risk of bleeding and bruising is expected to be increased in thrombocytopenic patients and will be minimized by the infusion of IVIG and/or platelets' transfusions before the procedure.

The risks associated with reduced intensity busulfan treatment are expected to be decreased compared to standard dose treatment. Busulfan toxicity includes myelosuppression, nausea,

vomiting, hair loss, mucositis, hepatotoxicity, seizures, hypo/hypertension, and lung fibrosis. Prolonged exposure to Busulfan may result in cataract formation, secondary tumors and sterility.

Fludarabine is a drug currently used in paediatric non-myeloablative preparative regimen in HSCT. Fludarabine toxicity includes bone marrow aplasia, nausea, vomiting, mucositis, and transient increase of liver enzymes. If given at high doses, Fludarabine can induce a progressive neurotoxicity due to demyelinating damage as main side effect. The patients enrolled in our clinical trial will receive lower doses of i.v. Fludarabine (standard dose in transplant: 100-150 mg/sqm). During a prolonged exposure to Fludarabine, transient visual disturbances and alterations of consciousness might occur: these scheduled events are described in literature as revertible with the drug's suspension.

ATG is an immunosuppressive drug approved in conventional conditioning as an agent inducing a selective decrease in T-cell count. Prior to and during ATG administration, adequate pre-medication will be dispensed to prevent anaphylaxis episodes or fever and chills, mainly described as occurring during initial infusions. Other common adverse effects include thrombocytopenia, leukopenia, headache, abdominal pain, nausea, diarrhoea, dyspnoea, and dizziness, reversible upon withdrawal. In addition, patients receiving ATG might develop severe infections resulting from over-immunosuppression. Particular caution will be adopted considering post-transplant lymphoproliferative disease. Thus, EBV-positive patients showing signs of viral reactivation after gene therapy, will receive appropriate pre-emptive therapy (Rituximab). Potentially increased risk of malignancy (non-Hodgkin's lymphoma, myeloma) has been reported as complication in long-term exposure of the drug.

The risks associated with Rituximab infusion include infusion reactions (that can be rarely fatal), nausea, vomiting, headache, wheezing, allergic reactions, severe muco-cutaneous reactions, LDH increase, hypo/hypertension. Cases of HBV reactivation and progressive multifocal leukoencephalopathy have been described after the use of this drug. Prior to Rituximab administration, adequate pre-medication will be dispensed to prevent anaphylaxis episodes or fever and chills, mainly described as occurring during initial infusions.

In case of microbiological contamination of bone marrow CD34+ cells, detected after the initiation of the conditioning regimen, culture will be stopped and the lot not released. A new lot will be prepared from mobilized CD34+ cells previously cryopreserved. Cells will be thawed, transduced and re-infused, as described in the IMPD, 3-7 days after the foreseen date.

Considering that the drug product consists of autologous cells, which are washed before cell infusion, no short-term toxicity is expected to occur. In this regard, it should be borne in mind that the infusion of autologous CD34+ cells from bone marrow or mobilized peripheral blood in children affected by haematological or oncological disorders usually does not cause side effects.

